##### **4.1 Primary Objective**

The primary objective is to demonstrate non-inferiority in the wound volume reduction rate of investigational group versus control group patients with open wounds that have extensive soft tissue damage.

##### **4.2 Secondary Objectives**

The secondary objectives are to compare the differences of time to completion of wound bed preparation, wound area reduction rate, wound clinical assessments, incidence of adverse events (AEs) / serious adverse events (SAEs) and device deficiencies in investigational group versus control group.

## 5 Study Design

### 5.1 Overall Study Design and Rationales

#### 5.1.1 Overall Study Design

This is a prospective, multicenter, randomized (1:1), open-label, parallel controlled, non-inferiority trial evaluating the efficacy and safety of V.A.C. VERAFLTM Dressing Kit versus Negative Pressure Wound Drainage Material (Guangdong Shuangling Pharmaceuticals Co., Ltd.) for wound bed preparation in open wounds with extensive soft tissue damage. This is a pre-marketing trial of V.A.C. VERAFLTM Dressing Kit in China for National Medical Products Administration (NMPA) registration. It is anticipated that the primary efficacy endpoint (wound volume reduction rate) of investigational group is non-inferior to that of control group. Up to 170 subjects who meet the eligibility criteria will be randomized to the investigational group or control group at the ratio 1:1.

Debridement is not permitted during study treatment. Therefore, subjects will only be enrolled following definitive surgical debridement (if serial debridement performed) of the target wound. The target wound for each subject in both groups will be treated for up to 14 days or until deemed ready for closure by the investigator (whichever occurs first). Following study treatment, the wound may be treated with any standard therapy selected by the physician, and then accepted secondary intervention for wound closure according to the wound bed preparation situation. The planned study period consists of the following visits: Screening (Day -3 to 0), Day of randomization (Day0), Dressing change visit(s), End of treatment visit. The following data in both groups will be recorded and collected: wound volume reduction rate, time to completion of wound bed preparation, wound area reduction rate, incidence of AEs / SAEs and device deficiencies. The efficacy and safety of V.A.C. VERAFLTM Dressing Kit in treating open wounds that have extensive soft tissue damage will be evaluated according above data.

## 5.1.2 Rationale

### 5.1.2.1 Rationale of Study Design

A prospective, multicenter, randomized, open-label, parallel group controlled, non-inferiority clinical trial design is adopted in this clinical trial, according to *Helsinki Declaration, Administrative Measures for the Registration and Filing of Medical Devices (2021)*, *Good Clinical Practice for Medical Device (GCP) (2022)*, and *Guideline for Clinical Trial Design of Medical Devices (2018)* released by NMPA and other appropriate regulations or guidelines.

### 5.1.2.2 Rationale of Control Group Selection

According to the *Guideline for Clinical Trial Design of Medical Devices (2018)*, for therapeutic devices, when *selecting* positive control, an approved equivalent product should be given priority, and the efficacy and safety of which have been clinical accreditation. If an equivalent product cannot be selected on the China market for reasonable reasons, a product that is as similar as possible can be used as positive control. Secondly, the standard treatment method can be considered.

Nowadays, there is no approved dressing with solution instillation namely the NPWTi-d therapy in China market. So, a NPWT therapy will be selected in the trial. A Negative pressure wound drainage material manufactured by Guangdong Shuangling Pharmaceutical Co., Ltd. is selected as the control group treatment device, which can apply the NPWT therapy with wall suction. This control device is widely used in clinical institutions in China to deliver NPWT.

### 5.1.2.3 Rationale of Target Wound Selection

Open wound with extensive soft tissue damage may refer to skin, muscle, tendon, nerves, blood vessels, etc. In damaged wound beds, cell necrosis, exudate secretion, and bacterial proliferation increase the chance of infection. Effective daily drainage of necrosis and timely use of anti-infective treatment can accelerate wound healing. Most patients with extensive soft tissue damage are not suitable for primary skin grafting or skin flap repair, but they need to treat soft tissue trauma first to promote granulation

tissue formation, and then proceed with secondary intervention according to the preparation of wound bed. Conventional procedure requires a longer treatment cycle and recovery time to be able to have secondary intervention. While using of NPWT insulates the air and sucks out the exudate and necrotic tissue in the wound bed through negative pressure, reducing infection at the wound, helping to shorten wound healing time and improve treatment effect. It is considered that NPWT for this kind of wound has potential therapeutic advantages. Also, the target wounds of subjects belong to the scope of indications for the investigational device.

#### **5.1.2.4 Rationale of Blinding Selection**

This trial is set as open label, since the inconsistent packaging appearance of the devices between the two groups, the investigators and the subjects could not be blinded.

In this trial, independent assessors will be blinded to reduce measurement bias from outcome indicator measurers. 3D images collected from each site will be aggregated into a single database. The aggregated images will be analyzed / measured by the independent assessor so as to achieve the blinding of independent assessors.

#### **5.1.2.5 Rationale of Primary Endpoint Selection**

In general, change in wound area or wound closure rate is the primary endpoint in certain wound therapy. But the purpose of using NPWT is to prepare wound bed, promote formation of granulation tissue, reduce the wound and take advantage of the subsequent secondary intervention. If the change in wound area is to evaluate wound improvement for a large area of soft tissue damage, not a superficial wound, the situation is difficult to reflect the improvement in the depth dimension of the wound. Because this type of wound requires a second intervention, the wound is not completely closed after using of the investigational device and the wound closure rate is not suitable. Therefore, change in wound volume is used to reflect the improvement of the wound after NPWT treatment. The endpoint is better for the indication and can reflect the clinical condition of the investigational device performance; many previous studies have used this endpoint for wound evaluation . In addition, the wound volume will

be measured by a 3D Wound Imaging System, and the acquired data are objective, which can reduce bias by operators and other factors.

#### **5.1.2.6 Rationale of Treatment Duration Selection**

In general, the duration to prepare the wound bed for the treatment of wounds in the target population using NPWT is generally no more than 2 weeks, and the subsequent intervention will be followed by other methods for secondary intervention. In combination with this clinical trial, just the performance of the investigational device is observed, so the longest treatment duration is chosen to be 14 days.

#### **5.1.3 Total Anticipated Duration of Clinical Trial and Rationale**

Total Anticipated Duration: It is anticipated that the trial duration will be 51 months, i.e. Aug 2019 to Nov 2023.

Rationale: The duration includes all sites initiation, subject recruitment, treatment and follow-up; as well as collection, statistical analysis of study data, and clinical study report development.

### **5.2 Selection of Subjects**

#### **5.2.1 Inclusion Criteria**

Only adult subjects meeting all of the following criteria to be considered for participation:

- (1) Subject voluntarily participate in the trial and sign the informed consent form, and is willing to comply with protocol and all visits
- (2) Is anticipated to be an inpatient for a minimum of 6 days
- (3) Age: between 18 years and 70 years
- (4) Patient with open wounds from various etiologies with extensive soft tissue damage after definitive surgical debridement and appropriate for NPWT
- (5) The minimum size of the wound as measured by 3D wound imaging prior to entry into the study is 8cm (in any dimension), minimum 1cm in width and 0.8cm in depth. i.e. the minimum wound size is 8cm×1cm×0.8cm. Only one wound per subject will be included in the study, regardless of how many wounds the subject

has.

- (6) Female subjects of reproductive potential must have a negative pregnancy test result and must not be lactating at the screening visit.
- (7) Subject must be willing and able to use a highly effective contraception method during study participation.

### **5.2.2 Exclusion Criteria**

Subject who meets any of the following criteria will be excluded from participation in the study:

- (1) Subject undergoing chemotherapy
- (2) Subject with known immunodeficiency
- (3) Subject with serious complications or serious systemic infection
- (4) Known bleeding disorder or has received or is planning to receive long-term anticoagulation therapy
- (5) Known allergic reactions/hypersensitivity to any of the study treatment dressings components
- (6) Target wound is a burn wound
- (7) A wound open for 6 months or more
- (8) The subject's targeted traumatic wound injury is a craniofacial wound
- (9) There is implant (such as cardiac pacemaker, bone nail, bone lamella, artificial joint, artificial bone) visible in the targeted wound.
- (10) If undermining or tunneling represents approximately 15% or more of the wound.
- (11) A wound with enteric fistulas.
- (12) Subject's targeted wound that is contraindicated with investigational device including:
  - a) Malignancy in the wound
  - b) Untreated osteomyelitis
  - c) Non-enteric or unexplored fistulas
  - d) Necrotic tissue with eschar remaining in the wound after surgical debridement

(once necrotic tissue or eschar is removed from the wound bed, subjects may be included)

- e) Unprotected, exposed blood vessel, anastomotic sites, organs, or nerves in direct contact with foam
- f) Thoracic or abdominal cavities
- g) Unexplored wounds that may communicate with adjacent body cavities

(13) Subject's targeted wound that is contraindicated with the control group device and not suitable for participating in the trial judged by investigator

(14) Participation in another device or drug study within the past 30 days before screening or during study participation

(15) Other subjects who are not suitable for participating in the trial judged by investigator.

(16) Wounds that require more than 2 images in order to capture the entire wound.  
NOTE: each image must not exceed 20 cm in any one direction.

(17) Wound presents on greater than 50% of the circumference of any part of the body (e.g. wound that wraps around >50% of a leg or arm).

### **5.2.3 Criteria and Procedures for Subject Withdrawal**

#### **1) Dropout Criteria**

Definition: A subject in the clinical trial who for any reasons fails to continue in the study until the last visit required of him/her by the study protocol.

If meet the following situations:

- Lost to follow-up.
- Subjects withdraw their informed consent and voluntarily withdraw from the trial:  
Subjects could withdraw from the trial voluntarily if they could not endure the AE, think the treatment is not effective, and want to take other treatments or without any reason.
- When the investigator judged that the risk is greater than the benefit if subject continues to participate in the trial, or the subject cannot continue the clinical trial

in the following conditions, for example a subject has abnormal organ dysfunction, allergic reaction, poor compliance, exacerbations, or a SAE needed to stop the trial treatment, and the subject should withdraw from the trial.

- The subject's target wound needs other treatment and should withdraw from the trial.
- If the target wound condition worsens (such as infection aggravated, anaerobic bacteria infection, etc.) in the use of investigational dressing or control dressing during the process of NPWT, after the investigator's evaluation of wound and treatment result, and if the surgical debridement is needed again, the NPWT will be stopped, the end of study assessments completed and the subject withdrawn from the study, then the target wound will be opened and debrided repeatedly, until the next intervention (such as delayed healing, surgical closure, graft et al) can be carried out.

Subjects have the right to withdraw from the trial at any time without any reason.

For all subjects terminate the trial in advance, the investigator should make every effort to obtain the reasons of withdrawal, e.g. AEs, unsuccessful correction therapy, withdrawing from the trial based on the investigator's judgment or other reasons, which should be recorded on the source documents. Subjects withdrawing from treatment in the trial should complete withdraw visit according to the schedule of visit procedure.

**Disposal of drop-out cases:** trial conclusion form and reasons of dropout should be completed in the related document for all dropout cases. The investigator should make every effort to contact subjects to ensure compliance, obtain reasons for subject dropping out, record complications and AEs and try to complete required evaluations.

## 2) Criteria for Trial/Trial Treatment discontinuation

Trial termination is defined as the trial discontinued without planned assessments of all subjects completed.

- The trial should be terminated when the device is found with no clinical significance during the trial;

- Major mistake of protocol is found during the trial resulting in difficulty to evaluate the efficacy and safety of the device;
- The trial should be terminated when major deviation occurs during the conduct of the trial resulting in difficulty to evaluate the efficacy and safety of the device if the trial continues;
- Requirement from sponsor (e.g. financial problem, administration problems. etc.);
- The administration department terminates the trial for some reasons;
- The ethics committee (EC) terminates the trial for protecting the rights and benefits of subjects;

When the trial is discontinued, new subjects will not be enrolled and enrolled subjects who have not completed the trial will be treated and visited according to the result of discussion of sponsor and the investigator.

#### **5.2.4 Time Point of Enrollment**

Before study specific screening assessments are performed, signed informed consent forms (ICF) must be obtained from subjects, then appropriate screening procedures will be conducted; and subjects will be taken to receive the 3D-wound imaging procedure of their wounds following the definitive surgical debridement performed (if applicable). At the end of the procedure, subjects who continue to meet all inclusion and no exclusion criteria will be included and randomized. The randomization point will be the time point of enrollment for subjects.

#### **5.2.5 Expected Duration of Each Subject's Participation**

The participation duration of each subject is defined as the duration from the time of subject to be enrolled in the trial to the last visit. For each subject, it is estimated that the screening duration is up to 3 days, anticipated treatment i.e. wound bed preparation duration is up to 14 days. In total, expected duration of each subject's participation is up to 17 days. During the period, all patients will have the initial dressing placement and a minimum of 2 dressing changes.

### 5.3 Evaluation Method

#### 5.3.1 Evaluation of Efficacy

##### 5.3.1.1 Primary Endpoint

###### (1) Wound Volume Reduction Rate (unit: %)

**Define:** wound volume change over 14 days or until deemed ready for closure by investigator (whichever occurred first).

**Formula:** wound volume reduction rate = (wound volume before initial study treatment – wound volume after study treatment 14 days or deemed ready for closure before 14 days) ÷ wound volume before initial study treatment × 100%.

**Measurement:** 3D Wound Imaging System, digital photos and three-dimensional photographs will be taken of the wound (without dressing) by assigned staff for all subjects.

Three-dimensional wound images will be captured for randomization visit, dressing change visit (s), and end of treatment visit using a specialized imaging system. Imaging guidelines, equipment, and supplies will be provided to the investigational sites by KCI. The 3D images collected from each site will be aggregated into a single database. The aggregated images will be analyzed /measured by the independent assessor. The independent assessor will determine and plot the wound perimeter, the clean, healthy viable tissue, and other tissue types for each image. The imaging software will be used to calculate wound length, width, depth, surface area, and wound volume. The values of these parameters/assessments will be used for calculations of the primary endpoint and the secondary endpoints. The 3D wound images should not be used to guide patient treatment.

**Evaluation time point:** Day of Randomization (Day 0), Dressing Change Visit (s), and End of Treatment Visit.

**Statistical method:** the difference of wound volume reduction rate between investigational group and control group will be evaluated to determine whether the primary endpoint of the investigational group is non-inferior to that of control group.

**Rationale:** please see Section 5.1.2.5.

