### **3.1.3.1 Summary of Animal, in Vitro Studies and Clinical Trials**

While there is broad acceptance and a large body of evidence that supports NPWTi-d (with V.A.C. VERAFLDTM Dressing Kit) as an important tool in aiding wound healing. Most evidence include animal studies, expert opinion, case reports, case series and involving prospective treatment groups compared with control.

In 2012, Anthony et al, compared continuous and periodic wound instillation in conjunction with negative pressure wound therapy using an agar-based model. Continuous instillation at a rate of 30 cc/hour with negative pressure showed isolated exposure of instillation fluid to wound beds in agar wound models with and without undermining and tunneling. In contrast, periodic instillation illustrated uniform exposure of the additive to the entire wound bed including undermined and tunnel areas, with increased staining with each instillation cycle. These findings suggest that periodic instillation facilitates more uniform exposure throughout the wound, including tunnels and undermining, to instillation solutions, thereby providing therapy consistent with the

clinician-ordered treatment.

In 2013, Lessing et al, found that a greater reduction in wound area and perimeter in NPWTi-d wounds compared to all NPWT wounds ( $P < .05$ ) by 3D images Analysis on porcine excisional wounds.

In 2011, a post marketing study using VAC. VERAFLTM Dressing in operatively debrided wounds, the results showed that there was no statistically significant difference in the time to wound deemed ready or closure or coverage between NPWTi-d (n=71) and NPWT(n=66) subjects (mean 6.8 vs 6.3 days, median 6 vs 5 days, respectively;  $p = 0.7105$ ) in the Per-Protocol Population (NCT01867580).

In 2013, Brinkert et al, collected 131 patients treated with V.A.C. VERAFLTM Dressing. Mean duration of NPWTi-d was 12~19 days. 98% of the cases, the wounds were closed after debridement and following the use of NPWTi-d.

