#### **5.5.3 Specification Direction for Use of Device**

- (1) For subjects with multiple wounds, the target wound can only be treated with the randomly assigned device and the other wounds will receive the standard wound treatment in the institution.
- (2) Placing the dressings in the target wound directly following the definitive surgical debridement (if applicable) according to the investigational or control device IFU.
- (3) During the subject's hospital admission, subjects will receive their assigned study

treatment without interruption until the wound is deemed ready for closure or up to 14 days (whichever occurred first).

- (4) For the investigational group, instillation solution (only normal saline) will be refilled by related staff as often as required. Canister changes for each group will be performed by related staff as often as required.
- (5) Dressing change frequency will be determined by the investigator based on the wound condition and clinical experience, and the frequencies of investigational and control group devices are the same (48-72h one change).
- (6) If the wound has been deemed ready for closure, study treatment will stop and subjects will then transition to receive institutional standard wound treatment at the discretion of the investigator.
- (7) If the secondary intervention condition of the target wound is not met after 14 days of treatment with the investigational device, the patient will receive further clinical treatment judged by the investigator re-evaluation according to the standard wound treatment in the institution.

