### **6.1.2 The Level of Significance and the Power of the Clinical Trial**

The level of significance is one-side 0.025. The power of the clinical trial is 0.8.

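### Primary wound volume is read at the unblinded investigator's readiness call or Day 14, so treatment time can differ by arm, and no common-time analysis is planned to show the effect

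*Protocol*

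**What the plan says.** Protocol 5.3.1.1 and SAP 15.1.1 define the primary variable as "wound volume change over 14 days or until deemed ready for closure by investigator (whichever occurred first"). Protocol 5.5.3 has subjects receive their assigned "treatment without interruption until the wound is deemed ready for closure or up to 14 days (whichever occurred first"). One judgement thus ends exposure and fixes the reading day.

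Protocol 5.1.2.4 says "the investigators and the subjects could not be blinded". It adds that "independent assessors will be blinded to reduce measurement bias from outcome indicator measurers". That protects the measurement of the image, not the day on which it is taken. Protocol 5.3.1.1 also says "The 3D wound images should not be used to guide patient treatment", so readiness is a clinical judgement. No objective criterion for it is given.

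The primary ANCOVA (Protocol 6.5.1, SAP 15.1.3) has terms for treatment, center, their interaction and wound-size stratum, and none for treatment days. No sensitivity analysis in SAP 15.1.4 uses a common reading time. SAP 6.1 keeps durations above 14 days in the PPS.

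Related information is planned elsewhere:
- volume and reduction rate by visit and arm, descriptively (SAP 15.1.3);
- time to readiness by log-rank and Cox (SAP 15.2.2);
- days treated by Wilcoxon (SAP 15.4);
- an exploratory mixed model of volume (SAP 16).

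None of these has a role in interpreting the primary result. SAP 16 promises a treatment difference for each visit, but neither its listed effects nor its sample code include treatment-by-timepoint. As written, the model yields one treatment difference common to all visits.

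**The concern.** If wounds are called ready on reaching a certain state, both arms are measured near that state however long they took. A slower device gains days and partly catches up. A faster one is stopped earlier and loses credit for further shrinkage. Either way the volume difference can move toward zero, which in a non-inferiority comparison can hide a real deficit. An unblinded call can also move the reading day in one arm only, which can push the difference in either direction.

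At stake is what a non-inferior result would mean. It would be a statement about volume at the end of treatment, but could be read as equal volume reduction over equal time. Section 5.1.2.5 defends volume against area and closure rate and does not discuss the variable reading time. Wound area reduction rate is read at the same moment and shares the problem.

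**Working it through.** **The plan's own figure.** Protocol 6.1.1 uses margin 0.20, SD 0.40, a true difference implicitly of 0, and 64 evaluable per arm. Protocol 6.1.2 states: "The level of significance is one-side 0.025. The power of the clinical trial is 0.8".
- Normal approximation: n = 2 × (1.96 + 0.842)² × 0.40² / 0.20² ≈ 62.8, so 63 per arm.
- With the t distribution: 64 per arm, power 0.801. The stated figure is reproduced.

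**Chance of declaring non-inferiority, by the expected difference as read.** SE = 0.40 × √(2/64) = 0.0707. The noncentrality is (d + 0.20)/0.0707, and the CI half-width is about 0.14.

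| Expected difference d | P(non-inferior) |
|---|---|
| 0 | 0.801 |
| −0.05 | 0.558 |
| −0.10 | 0.289 |
| −0.15 | 0.104 |
| −0.20 | 0.025 |

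**Model A (assumed).** Volume reduction at day t is 1 − exp(−kᵢt), with log-normal kᵢ (log SD 0.5). Visits are every 2.5 days, the midpoint of the 48-72 h in Protocol 5.5.3, with a cap at Day 14. Readiness corresponds to a reduction of c = 30%, 40% or 60%. The control rate is set so that median time to c is 5.5 days, between the medians of the post-marketing study in Protocol 3.1.3.1 ("mean 6.8 vs 6.3 days, median 6 vs 5 days, respectively"). For c = 40%, the control rate is −ln(0.6)/5.5 = 0.093 per day. The test rate is set to give a deficit of exactly 20 points on a common day (5.5, 7 or 14). A share of readiness calls follows volume; the rest are made at a time unrelated to it.

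| Share of calls tracking volume | Deficit as read (points) | P(non-inferior) |
|---|---|---|
| All | 5 to 11 | 0.24 to 0.57 |
| Half | 10 to 17 | 0.06 to 0.30 |
| None | 15 to 23 | 0.01 to 0.11 |

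One row as an example: c = 40%, common day 7, all calls tracking volume. The test rate is 0.49 of control, mean treatment is 11.5 against 7.3 days, the deficit reads as 6.9 points, and P is 0.450. Over all rows in which every call tracks volume, the slower arm averages 10.9 to 13.2 days against 7.3, and 34 to 75% of it reaches the cap. The cap is why convergence is partial. With no link, the deficit scatters around 20 because stopping times differ from the chosen common day; it does not shrink systematically.

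In the other direction, a true 20-point benefit on a common day reads as 4 to 6 points when every call tracks volume. Superiority power then falls from 0.80 to 0.09 to 0.14. For c = 60% and Day 14, a 20-point benefit is not attainable in the model.

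**Model B (assumed, separate check).** Mean control rate 0.14 per day (CV 50%), readiness at 45% reduction (SD 10%), visits at random 2- or 3-day gaps, cap at Day 14. Control stops at mean 6.7 and median 6 days. Cells give reduction in test against control.

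| Test speed | End of treatment | Day 6 | Second change | Mean days |
|---|---|---|---|---|
| 50% | 46.5 vs 53.2 (−6.7) | 33.0 vs 53.5 (−20.5) | 28.2 vs 44.3 (−16.1) | 10.4 vs 6.7 |
| 70% | 50.2 vs 53.2 (−3.0) | 42.3 vs 53.5 (−11.2) | 35.9 vs 44.3 (−8.4) | 8.5 vs 6.7 |

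With control rates of 0.08 to 0.10 per day and half speed, the endpoint shows −9 to −11 points against −16 to −18 at Day 6. Two changes of assumption remove most of the effect. With readiness timing unrelated to volume, half speed reads −20.5 at end of treatment. With an 80% readiness threshold (control mean about 12 days), it reads about −18.

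**Differential open-label timing.** In Model A with equal healing, calling the test arm 2.5 days later moves the difference by +10 to +11 points; calling it 2.5 days earlier moves it by −11 to −16. A shift of +10 lies 0.10 above the superiority boundary of zero. By the first table (the same distance as −0.10 from −0.20), superiority would then be declared with probability about 0.29.

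**The case against.** The main objection is that convergence is an assumption. The documents never say that readiness follows volume. The goals in Protocol Table 3-1 include removing contamination, decreasing exudate and covering exposed structures, and the 3D images may not guide care. This stands: without a link there is no systematic convergence. However, the same table lists wound fill among the goals, so some link is plausible.

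Second, the 5-to-6-day medians are only one of the durations cited. Protocol 3.1.3.1 also reports a 131-patient series with mean therapy of 12 to 19 days, section 3.1.2 cites 10 to 14 days, and section 5.1.2.6 says generally no more than two weeks. If most wounds run to the cap, the reading is nearly at a common time. This stands too.

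Third, a reader might infer that a half-speed device would routinely pass, since −6.7 lies inside the margin. The rule applies to the lower confidence limit. At −6.7 the expected limit is −6.7 − 14.0 = −20.7, and non-inferiority is declared about 46% of the time. That is inflated, but not routine.

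Fourth, a reader might infer that the bias always favours non-inferiority, or that the plan ignores speed. Neither is supported: differential timing can act either way, and speed is compared in SAP 15.2.2 and 15.4. What is missing is any link from those results to the primary one. Time to readiness also rests on the same unblinded call.

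Finally, volume at end of treatment is a legitimate quantity, which is a reason to keep it and to name it accurately.

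**Conclusion.** The concern holds in conditional form. It is certain from the documents that the reading time depends on the outcome, that the person setting it knows the arm, and that neither the primary model nor any listed sensitivity analysis uses a common time. The size is not certain. It runs from little or no convergence (no link to volume, or most wounds at Day 14) to a 20-point common-day deficit read as about 5 to 11 points, with the chance of declaring non-inferiority at 0.24 to 0.57 instead of 0.025. The upper end assumes exponential shrinkage, readiness fully determined by volume, median control readiness near 5.5 days, 64 per arm and SD 40 points. Differential open-label timing is a separate risk in either direction.

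A reader might go further and conclude that the primary endpoint is invalid or must be replaced. The documents do not support that. A plain Day 14 reading would also be hard to interpret, because study treatment stops at readiness and other care follows (Protocol 5.1.1, 5.5.3). The gap is one of supportive analysis and wording, and should be closed before database lock.

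**What to change.** Keep the primary endpoint, margin and decision rule.

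1. In SAP 15.1.4 and Protocol 6.5.1, pre-specify a supportive ANCOVA with the same terms, on the PPS and FAS, of volume reduction at the second dressing-change image. At 48-72 h spacing this falls at about Day 4 to 6, and Protocol 5.2.5 plans that "all patients will have the initial dressing placement and a minimum of 2 dressing changes". For subjects who stopped before it, use the end-of-treatment image and state how many there were, by arm.
2. Report that difference and its 95% CI beside the primary result and time to readiness, without a pass/fail margin. Protocol 6.1.5 justifies −0.20 only for the primary endpoint. At 64 per arm and SD 40, a truly identical device would miss such a margin about 20% of the time (1 − 0.801).
3. Add treatment-by-timepoint to the SAP 16 model, so that it can give the per-visit differences it promises.
4. Do the same for wound area.
5. Word the primary conclusion as volume reduction at end of treatment, not over equal treatment time.

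The cost is wording and one more run of an existing model. The images are already taken at every dressing change and measured by the blinded assessor. Sample size and clinical management do not change. The downsides are an extra result that may be less favourable, and some remaining outcome-dependent timing among early stoppers (14% of controls in one run of Model B).
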